10.2.1.1 Preoperative Elements

- Mechanical bowel preparation plus oral antibiotics should be used.
 - Note, laxatives and oral antibiotics used for mechanical bowel preparation are

permitted in the preoperative period (See [Section 9.6.1](#))

- Preemptive, multimodal antiemetic prophylaxis (i.e., ondansetron and dexamethasone) must be used for all at-risk subjects (i.e., ≥ 2 risk factors [female gender at birth, nonsmoker, history of motion sickness or postoperative nausea and vomiting (PONV), postoperative opioid use]).
- A multimodal, opioid-sparing, pain management plan should be planned as appropriate (e.g., combination of acetaminophen and NSAIDs, gabapentin administered at a low dose).
 - **Note:** although an opioid-sparing approach should be used for postoperative pain management, opioid analgesics use is not prohibited.
- Alvimopan, methylnaltrexone, naloxone (except for treatment of known or suspected opioid overdose), and prophylactic or routine use of metoclopramide are prohibited for the purposes of this protocol in order to reduce confounding of the effect of TU-100 on the primary outcome measure.

10.2.1.2 Intraoperative Elements

- Excess fluid administration and volume overload should be avoided.
- Transverse abdominis plane (TAP) blocks (with bupivacaine or bupivacaine liposome injectable) are permitted.
- Epidural anesthesia should not be used for the purposes of this protocol in order to reduce confounding of the effect of TU-100 on the primary outcome measure.

10.2.1.3 Postoperative Elements

- A multimodal, opioid-sparing, pain management plan should be implemented as appropriate (e.g., combination of acetaminophen and NSAIDs).
 - Gabapentinoids (i.e., gabapentin, pregabalin) should not be used unless indicated for postoperative neuropathic pain. (See [Section 9.6.1](#))
 - **Note:** although an opioid-sparing approach should be used for postoperative pain management, opioid analgesics use is not prohibited.
- Indwelling NGTs for *prophylaxis* cannot be used.
- Protocol guidelines for selective postoperative nasogastric intubation for the management of clinical events should be followed, as shown below.
 - Occurrence of one or more of the following events:
 - ≥ 2 low-volume (e.g., < 300 cc) episodes of emesis
 - ≥ 1 high-volume (e.g., ≥ 300 cc) episode of emesis
 - Moderate to severe abdominal distension
- IV fluids are to be discontinued as soon as the subject can tolerate oral liquids and maintain adequate hydration.

- Begin oral feeding early unless otherwise contraindicated.
- Subjects must be mobilized early, starting from Day 1 unless otherwise contraindicated.
- For the purposes of this protocol, in order to reduce confounding of the effect of TU-100 on the primary outcome measure, the following interventions are prohibited:
 - Alvimopan, methylnaltrexone, naloxone (except for treatment of known or suspected opioid overdose)
 - Routine use of laxatives and stool softeners
 - Prophylactic use of prokinetics (e.g., metoclopramide, cisapride, domperidone, erythromycin used as a prokinetic agent)
 - Sham feeding (e.g., gum chewing)

10.2.2 Screening Period

Screening (Day -28 to Day -1 [day of surgery])

Subjects will be consented and screened for eligibility. Screening will include a brief interview (including demographics, medical history [including previous abdominal surgeries and acute or chronic hepatic conditions], and prior medication), serum pregnancy test, vital signs, physical examination, laboratory testing (including hematology, chemistry, LFTs, serology [hepatitis B virus (HBV) and hepatitis C virus (HCV)], and urinalysis) and ECG. Subjects who do not satisfy all eligibility criteria will be recorded as screening failures.

Additional screening questions for COVID-19 will be asked by the investigator or site staff:

- 1) Has the subject traveled to countries known to be COVID-19 hotspots as well as US cities with high COVID-19 case densities, within the last 14 days before screening?
- 2) Does the subject currently have or did the subject have flu-like symptoms within the past 72 hours, e.g., fever, cough, shortness of breath?
- 3) Has the subject had any close contact with any person exhibiting flu-like symptoms within the past 14 days?
- 4) Has the subject been exposed to anyone who has been diagnosed with COVID-19 within the past 14 days?

Retesting during the screening period

If the results of the blood tests (hematology, chemistry) are $< 1.5 \times \text{ULN}$, not associated with an acute or chronic clinical condition or comorbidity and considered by the PI to be non-clinically significant, a new sample can be collected for a retest. Exclusionary liver function test levels may be retested once within 14 days of the original screening date, but only with the documented approval of the Sponsor's medical monitor. Only 1 retest will be allowed within the screening period. If the results of the retest fall within the normal range (i.e., DO NOT meet protocol exclusion criterion #19 for abnormal liver tests) the patient may be considered for randomization assuming all other protocol-specified criteria are met including the PI's clinical judgement. The PI should contact the medical monitor should he/she have any questions or issues for discussion in these cases prior to patient randomization.

Exceptional measure for COVID-19

This document is confidential.

- Please follow your local testing guidelines for SARS-CoV-2. If testing is mandatory at your institution, a positive result would be exclusionary
- Subjects with prior history of COVID-19 must be confirmed recovered per CDC criteria and have a SARS-CoV-2 negative test result
- If a subject contracts COVID-19 during the interval between screening and pre-surgery Day -1 (and falls out of the screening window), he or she may be rescreened once recovered, assuming the subject meets all other inclusion/exclusion criteria and per investigator clinical judgement

Depending on the COVID-19 situation (and/or to reduce burden of patient travel as needed, e.g., need to travel long distances to the site), measures below may be considered for the screening:

- Consider performing laboratory testing, urine pregnancy tests, and safety laboratory tests at a local hospital, or regional independent laboratory located near the subject.
- Telephone conversation or video conferencing may be used for obtaining information on demography, medical and surgical history, and prior and concomitant medications.
- Local at-home services performed by trained non-study personnel may be used for measurement of vital signs, physical examinations, and ECG.

If physical examination, screening day laboratory tests, 12-lead ECG, and serum pregnancy test have been performed within 28 days before surgery, but before consent is obtained, the full physical examination, screening laboratory tests, 12-lead ECG, and serum pregnancy test will be reviewed and need not be repeated unless deemed appropriate by the investigator. A review of the physical examination with revision or addition of any changes, if required, will be performed after the consent has been signed.

The Schedule of Assessments is located in [Table 1](#).

Day -1 (Day of surgery)

LFTs will be assessed pre-surgery, unless performed within 14 days of Day-1 and results were within normal limits.

The following procedures will be completed on the day of surgery:

- Capture additional medical history since screening
- Record concomitant medications (pre- and post-surgery)
- Perform a urine pregnancy test for WOCBP only
- Monitor prespecified postoperative complications
- Record surgery start (as noted from operating room records) and stop dates and times (time of the last suture or staple)
- Record need for blood transfusion
- Record estimated blood loss
- Record total intraoperative IV fluid type and volume

- Record NGT removal, if used intraoperatively

All subjects will be managed with an ERAS protocol as per hospital SOC. However, elements within ERAS protocols intended to manage GI recovery will be standardized and compliance measured to the extent possible within this trial (see [Sections 10.2.1](#)).

Screened subjects should be instructed to call ahead before they come for scheduled surgery if they have COVID-19 symptoms or are sick to help the PI team reschedule their surgery and associated study procedures.

10.2.3 Treatment Period

Day 1 (postoperative Day 1, day of randomization)

On the day after surgery, eligible subjects will be randomly assigned (1:1:1) to receive TU-100 15 g/day, 7.5 g/day, or placebo if subjects meet randomization criteria as described in [Section 8.4](#). Subjects will be stratified based on surgical approach (open versus laparoscopic).

Samples for routine clinical laboratory tests (including hematology, chemistry, LFTs, and urinalysis) should be taken before study drug administration to represent baseline values. An ECG should be performed on Day 1.

Day 1 (postoperative Day 1) up to Day 10 (postoperative Day 10) or hospital discharge (whichever occurs first)

After randomization, subjects will be provided with an eDiary and given instructions for use. The diary will be used by subjects to record both clinical (e.g., time and occurrence of flatus or BM) and subject-related outcomes (e.g., symptoms associated with delayed GI recovery, such as nausea, vomiting/retching, abdominal bloating). Daily entries in the subject eDiary will be made at the hospital from the day of randomization throughout the entire hospitalization period.

Subjects will record the following items in their eDiaries on all postoperative in-hospital study stays (Day 1 up to Day 10)

- First flatus (record in real time)
- First BM (record in real time)
- Nausea occurrence and bothersomeness (24-hour reflection)
- Vomiting/retching occurrence/number of episodes (24-hour reflection)
- Abdominal bloating occurrence and bothersomeness (24-hour reflection)

The following procedures will be performed on all postoperative in-hospital study stays (Day 1 up to Day 10)

- Administer study medication by mouth TID (3 times per day [i.e., 6 hours \pm 1 hour apart]) until hospital discharge or for a maximum of 10 days
 - **Note:** Dosing will be in-hospital only. Dosing will occur approximately every 6 hours (\pm 1 hour) and will be administered by study coordinator or floor nurse
 - Record time of dosing

- Perform GI assessments (twice daily, morning and afternoon; assessments must be separated by at least 6 hours)
- Record time of GI assessment, and also:
 - Record time of first:
 - Clear liquid toleration
 - Solid diet toleration
 - Absence of distention and presence of bowel sounds and flatus (i.e., time of when all 3 conditions have been achieved)
 - Record time subject is ready for hospital discharge (based solely upon recovery of GI function as determined by the treating medical team)
- Time of discontinue IV fluids and transition to oral liquids
- Time of transition to oral analgesics
- Record concomitant medications
- If an NGT is inserted, record date, time, and reason for insertion
- Monitor AEs
- Review of hepatobiliary AEs
- Monitor prespecified postoperative complications (See [Section 11.7](#))
- Collect LFT samples on Day 4, Day 7, and Day 10 (if subject remains in the hospital) per [Table 1](#).
- Collect blood samples for PK analyses only at designated sites at:
 - 1 hour (\pm 30 minutes) after the first dose on Day 1
 - 4 hours (\pm 1 hour) after the first dose of Day 1
 - Predose on Day 3*
 - 2 hours (\pm 1 hour) on Day 3*
 - Predose on Day 5*
 - 2 hours (\pm 1 hour) on Day 5*

*if not discharged yet

In addition, PK samples should be taken at early termination. If a subject is terminating early on a day scheduled for a blood draw, a second sample on the day of termination should be taken if possible. If a subject is terminating early on a day not scheduled for a blood draw, at least 1 sample should be obtained that day if possible.

All subjects will be managed with an ERAS protocol as per hospital SOC. However, elements within ERAS protocols intended to manage GI recovery will be standardized and compliance measured to the extent possible within this trial. ([Section 10.2.1](#)).

Hospital discharge or study withdrawal/termination

Subjects will record the following items in their eDiaries on hospital discharge/study termination day:

- First flatus (record in real time)
- First BM (record in real time)
- Nausea occurrence and bothersomeness (24-hour reflection)
- Vomiting/retching occurrence/number of episodes (24-hour reflection)
- Abdominal bloating occurrence and bothersomeness (24-hour reflection)

The following procedures will be performed at the hospital discharge/study termination visit:

- Perform physical examination, including weight. Any clinically relevant physical abnormalities (with the exception of surgical scars) that were not present at screening should be recorded as AEs
- Record vital signs (blood pressure, heart rate, respiratory rate, and temperature)
- Obtain 12-lead ECG
- Collect blood samples for hematology and serum chemistry, LFTs and a urine sample for urinalysis
- Collect blood samples for PK testing at early termination (not necessary for normal hospital discharge). If a subject is terminating early on a day scheduled for a blood draw, a second sample on the day of termination should be taken if possible. If a subject is terminating early on a day not scheduled for a blood draw, at least 1 sample should be obtained that day if possible. Record time of blood sampling.
- Perform GI assessments
 - Record time of GI assessment
 - Record time of first:
 - Clear liquid toleration
 - Solid diet toleration
 - Absence of distention and presence of bowel sounds and flatus (i.e., time of when all 3 conditions have been achieved)
 - Record time subject is ready for hospital discharge (based solely upon recovery of GI function as determined by the treating medical team)
- Review records relating to hospital discharge: date and time that discharge order was written (order must be written the same day that discharge is expected to occur)
- Record concomitant medications
- Monitor AEs
- Monitor prespecified postoperative complications

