8.4 Randomization Criteria

In order to be randomized, a subject **MUST** meet the following criteria:

1. Underwent an eligible surgery (Inclusion Criterion #4)
2. NGT tube has been removed, if inserted intraoperatively
3. Is able to receive oral medications

Additionally, in order to be randomized, a subject **MUST NOT** have achieved both upper and lower GI components that comprise the primary efficacy endpoint **before Day 1 Randomization**, as listed below:

Upper GI

4. Transitioned from clear liquids to full liquids and/or solid food

Lower GI

5. Had first BM

OR

Achieved all 3 events below:

- a) Absence of abdominal distension; AND
- b) Experienced first flatus after surgery; AND
- c) Presence of bowel sounds after surgery

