11.2 Gastrointestinal Assessments

Gastrointestinal assessments will be performed twice daily in the morning and afternoon, starting on randomization Day 1, and continuing until hospital discharge or study termination.

Assessments must be separated by at least 6 hours. Gastrointestinal assessments will include:

- Recording time of first:
 - Clear liquid toleration (i.e., time at which the subject transitions from clear liquids to the next diet stage [full liquids or solids])
 - Solid diet toleration (i.e., able to eat a meal that requires chewing without a vomiting episode by the time the next consecutive meal is offered)
 - Note, if the first solid meal is consumed on the day of hospitalization (i.e., the day of surgery), the time to toleration of solids is as stated (e.g., the time to eat solids without a vomiting episode by the time the next consecutive meal is offered). Further, if the first solid meal is consumed on the day of discharge, the time to toleration of solids criteria is met if there is no vomiting prior to discharge. In all cases, the actual time that should be recorded on the eCRF is the time the meal was consumed by the subject, not the cutoff time for vomiting prior to next consecutive meal or discharge.
 - Absence of distention + presence of bowel sounds + flatus (time of when all 3 conditions have been achieved)
- Record time subject is ready for hospital discharge (based solely upon recovery of GI function as determined by the treating medical team)

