11.3 Electronic Diary Assessments

Subjects will record in their eDiaries on all postoperative in-hospital days. They should record the following:

- First flatus (record in real time)
- First BM (record in real time)

- Nausea occurrence and bothersomeness (a 24-hour reflection)
- Vomiting/retching occurrence/number of episodes (a 24-hour reflection)
- Abdominal bloating occurrence and bothersomeness (a 24-hour reflection)

The investigator will assess eDiary entries at study visits starting on Randomization Day 1 and continuing daily until hospital discharge or study termination.

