14.5.2 Analysis of Primary Efficacy Endpoint

The primary efficacy variable is time to gastrointestinal recovery (TGIR), a composite endpoint defined as the following:

TGIR = maximum (time to first toleration of liquids; time to first BM OR [absence of distention AND bowel sounds AND flatus])

Time to an event is defined as the elapsed time, in hours, from the end of surgery to the time of the first event, to be calculated as:

$$\text{Time to event (hours)} = (\text{time of the event} - \text{time of end of surgery})$$

When TGIR is greater than 10 days (240 hours), it will be censored at 10 days. Censoring rules for other secondary time-event endpoints will be discussed in the SAP.

The primary analysis of TGIR will be based on the Cox proportional hazard model (Cox PH) that includes the main effects for treatment and surgical approach (open versus laparoscopic). The estimates of time to event for the quartiles (25%, 50%, 75%), hazard ratios and their corresponding one-sided 95% confidence intervals (CIs), the Wald Chi-square one-sided *P* values from the Cox analysis will be summarized. The ties in the data will be handled by the Breslow method.

A secondary analysis will be applied for TGIR using the Cox PH model including main effects for treatment, surgical approach (open versus laparoscopic), and covariates such as surgical type, gender, age (years), post-operation opioid consumption (mg morphine equivalents; [APPENDIX 2](#)), thoracic epidural use, and surgery duration (hours). Backward method will be used to select statistically significant covariates (*P* < 0.1). Adjusted *P* value and HR will be provided after the final model is selected.

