15.2 Data Handling

Any data to be recorded directly on the eCRFs (to be considered as source data) will be identified at the start of the study. Data reported on the eCRF that are derived from source documents should be consistent with the source documents, or the discrepancies must be explained. See also [Section 15.3](#).

Subjects will be given eDiaries in which to record events specified in [Section 11.3](#) on postoperative in-hospital days. The eDiary entries are considered source data. Data will be transferred from the eDiaries into the clinical database for analyses.

Clinical data will be entered by site personnel on eCRFs for transmission to the Sponsor. Data on eCRFs transmitted via the web-based data system must correspond to and be supported by source documentation maintained at the study site, unless the study site makes direct data entry to the databases for which no other original or source documentation is maintained. In such cases, the study site should document which eCRFs are subject to direct data entry and should have in place procedures to obtain and retain copies of the information submitted by direct data entry. All study forms and records transmitted to the Sponsor must only include coded identifiers such that directly identifying personal information is not transmitted. The primary method of data transmittal is via the secure, internet-based electronic data capture (EDC) system maintained by Syneos Health. Access to the EDC system is available to only authorized users via the study's internet website, where a user unique assigned username and password are required for access.

Any changes made to data after collection will be made through the use of the EDC system. Electronic case report forms (eCRFs) will be considered complete when all missing and/or incorrect data have been resolved.

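### The protocol names no source for the time of a first bowel movement between end of surgery and randomization, although such subjects can be randomized and the clock starts at end of surgery

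*Combined protocol and SAP*

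**What the plan says.** **Clock.** Section 14.5.2: "Time to an event is defined as the elapsed time, in hours, from the end of surgery to the time of the first event". TGIR is the larger of the upper time (clear-liquid toleration) and the lower time. The lower component is met by a first BM or by the three-sign criterion (no distension, bowel sounds, flatus).

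**Who can be randomized.** Section 8.4 says a subject must not "have achieved both upper and lower GI components that comprise the primary efficacy endpoint" before randomization on Day 1. Having only one component is not a bar. The check includes whether a first BM has occurred. It does not ask when.

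**Where BM is timed.** Sections 10.2.3 and 11.3 and the Table 1 footnotes put first BM, recorded in real time, in the eDiary. On its start, Section 10.2.3 says: "After randomization, subjects will be provided with an eDiary and given instructions for use", and "Daily entries in the subject eDiary will be made at the hospital from the day of randomization throughout the entire hospitalization period". Section 15.2 adds: "The eDiary entries are considered source data".

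**What staff time.** Section 11.2: "Gastrointestinal assessments will be performed twice daily in the morning and afternoon, starting on randomization Day 1". The times listed there are clear liquids, solids, the three-sign criterion and readiness for discharge. BM is not among them. The day-of-surgery list in Section 10.2.2 has no BM or flatus time, and the eDiary and GI-assessment rows of Table 1 are unmarked in the post-surgery column.

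**The concern.** Between end of surgery and randomization there is a window in which the endpoint clock is running but no stated procedure times a BM. The protocol foresees milestones in that window. Section 8.4 asks about a BM, and Sections 6.2.2 and 11.2 give a timing rule for a solid meal eaten on the day of surgery. There is no counterpart for BM.

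Three endpoints use first-BM time: time to first BM, GI-2 recovery and TGIR. For a subject with an early BM the database could hold no time, a later BM logged as the first, or a time that the site adds on its own initiative. With up to about 55 sites, practice may differ. A later BM logged as the first falls after dosing, so a pre-treatment event would be exchanged for one that treatment can influence. A time that was never collected cannot be recovered by an analysis rule written later.

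**Working it through.** **1. The plan's own figure.** Section 14.2 gives about 87% power at HR 1.428, one-sided alpha 0.05. With 366 / 3 = 122 evaluable subjects per arm, a pairwise comparison has 244. Taking all as events (Schoenfeld):

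power = Φ(√(244/4) × ln 1.428 − 1.645) = Φ(7.810 × 0.3563 − 1.645) = Φ(1.138) = 0.872.

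The stated power reproduces. Nothing in it depends on how BM is timed.

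**2. Which endpoints can be wrong.** Let U be clear-liquid toleration, S toleration of solids, T the three-sign time, B an early BM before randomization, and B′ the next BM (infinite if none is logged).

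- Time to first BM: the true value is B. Using B′ is wrong for every early-BM subject.
- GI-2: the true value is max(S, B). Using B′ gives max(S, B′), which differs when B′ > S (given S > B). There is no alternative lower route.
- TGIR: an eligible subject with an early BM has not yet met the upper component, so U > B and the true TGIR is max(U, min(B, T)) = U. Using B′ gives max(U, min(B′, T)), which differs only if B′ > U and T > U.

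Example with assumed times: randomization at 20 h, U = 30 h, B′ = 20 + 18 = 38 h. True TGIR is 30 h. If T = 45 h, substitution gives max(30, min(38, 45)) = 38 h. If T = 30 h, it gives max(30, min(38, 30)) = 30 h, unchanged.

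**3. Size.** The documents give no distribution for the components. Both sets below are assumptions. Both suppose that a later BM is substituted in every early-BM subject.

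| | Set A | Set B |
|---|---|---|
| Time distributions | independent log-normal | independent exponential |
| Randomization after surgery | 20 h | 18 to 26 h |
| Median U | 30 to 48 h | 30 h |
| Median BM | 36 to 60 h | 40 to 100 h |
| Median T | 30 to 60 h | 24 to 48 h |
| Randomization to next BM | mean 18 h | median 18 to 24 h |
| TGIR altered, share of all randomized | about 0.4% to 5.4% | about 1.4% to 6.0% |
| Shift in overall median TGIR | 0 to 0.8 h | 0.3 to 1.9 h |

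In Set A about 3% to 16% of randomized subjects have an early BM, and TGIR changes in 11% to 41% of those. Multiplying within scenarios gives the share of all randomized: at the low end 0.033 × 0.12 = 0.4%, at the high end 0.136 × 0.40 = 5.4%. Averaged over early-BM subjects, recorded time to first BM moves by about 22 to 23 h and TGIR by about 1 to 6 h.

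**The case against.** The strongest reply is that nothing in the protocol tells anyone to log a later BM as the first. The endpoint is defined by the first event, the site must already know at the Section 8.4 check whether a BM has occurred, and under Section 11.3 the investigator reviews diary entries daily from Day 1, so a mislabelled entry could be caught. The eCRF is not in the file, nor is a separate SAP. The protocol leaves detailed missing-data rules, secondary censoring rules and TGIR sensitivity analyses to the SAP, which prevails over the protocol where they differ (Section 14.1).

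Much of this stands. A reader might infer that an early BM is always replaced by a later one. The documents do not say so: it may also be missing, or entered by the site. A reader might also infer that TGIR is wrong for every such subject. It is not, because TGIR is a maximum with a second lower-GI route that staff assess twice daily. Leaving that route out of Set B raises the altered share to about 3.3% to 9.7%, but it also gives a placebo median TGIR of about 70 to 120 h against the planned 48 h, so it does not describe this endpoint. Nor is a false-positive result shown. Early BMs precede randomization and are balanced between arms in expectation, and with no drug effect substitution creates no expected difference.

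What the reply does not supply is the time itself. Knowing that a BM occurred does not date it, daily review of a diary issued later does not date it, and an SAP rule can use only what was collected.

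**Conclusion.** The gap is real but narrow. As written, the protocol names no source for the time of a BM between end of surgery and randomization and no rule for using one. The main exposure is time to first BM, for every early-BM subject, followed by GI-2. For TGIR the exposure is limited to subjects whose later BM and three-sign time both follow clear-liquid toleration. The effect on median TGIR is probably about 0 to 2 h. That range rests on assumed distributions, an assumed randomization time and substitution in every case. Sample size, alpha and the stated power are unaffected. The change is worth making because it is cheap and can be made only while data are being collected.

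**What to change.** - At the Day 1 randomization-eligibility check, record on the eCRF the date and time of any first BM and any first flatus since end of surgery.
- State in Section 11.2 and in the SAP that first-BM time is the earlier of this entry and the eDiary entry.
- State in the same places that lower-GI time for TGIR is the earlier of first-BM time and the three-sign time.

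The cost is two date-and-time items at a check the site already makes, plus two sentences of text. The small downside is that times before randomization will come from recall or nursing notes, and so will be less exact than real-time diary entries.
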